11.5.2 Safety

Vital signs

All vital signs data will be listed by treatment, patient, and time point and abnormalities will be flagged. Summary statistics will be provided by treatment and time point, for the SAF (up to Day 90), and for SAF1 and SAF2 separately.

To assess the effect of LNP023 on blood pressure after dosing with LNP023, blood pressure and heart rate at 1-2 hours post dose on Day 1 and Day 30 (see [Assessment schedule](#)) expressed as change from baseline will be summarized, for the SAF. This represents the blood pressure at the approximate time of C_{max} after first dose and at steady state. The relationship between changes in blood pressure and heart rate and the C_{max} concentrations will also be investigated graphically.

ECG

All ECG data will be listed by treatment, patient, and time point, and abnormalities will be flagged. Summary statistics will be provided by treatment and time point, for the SAF (up to Day 90) and for SAF1 and SAF2 separately; the number of patients with values above key threshold values will be displayed.

Clinical laboratory evaluations

All laboratory data will be listed by treatment, patient and time point, and if normal ranges are available abnormalities will be flagged. Summary statistics will be provided by treatment and time point, for the SAF (up to day 90) and for SAF1 and SAF2 separately.

Adverse events

All information obtained on AEs will be displayed by treatment and patient.

The number and percentage of subjects with adverse events will be tabulated by System Organ Class (SOC) and Preferred Term (PT) with a breakdown by treatment, for the SAF (up to day 90) and for SAF1 and SAF2 separately. A subject with multiple AEs events within a SOC is only counted once towards the total of this SOC for the event of highest severity.

Exposure-adjusted AE summaries will also be likewise considered.

Summaries of SAEs will be provided in a similar manner.

Further displays of AEs may be produced in order to appropriately describe the outcomes seen in this trial.

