1.4 Study design and treatment

This is a multicenter, randomized, double blinded (investigator, subject and sponsor blinded), placebo-controlled, dose-ranging, parallel-group adaptive design.

The study comprises a run-in phase of at least 30 days (the run-in phase can be extended to minimize patient risk of visit sites during the COVID-19 pandemic), a 90 days treatment phase in Part 1; a 180 days treatment phase in Part 2 and a 90 days follow-up phase, for both Parts 1 and 2. All baseline safety evaluation results must be available prior to dosing. Drug administration and treatment period will start on Day 1.

Design of Part 1:

[figure not shown]
Approximately forty-eight (48) patients will be enrolled in Part 1 to allow for 40 patients to complete this part of the study. These patients will be randomized to one of four treatment groups as follows, with study treatment administered in all twice daily (b.i.d):

- 14 patients to placebo,
- 10 patients to LNP023 10 mg,
- 10 patients to LNP023 50 mg and,
- 14 patients to LNP023 200 mg

The patients who have been randomized to Part 1 will not be able to participate in Part 2 of the study.

Figure 1-1 depicts the study design for Part 1 and the study duration for patients will be maximum 270 days.

Figure 1-1: Study Design for Part 1

Design of Part 2:

An interim analysis (IA) will be performed when approximately 48 patients have been randomized in Part 1 and have completed treatment to Day 90 (or withdrawn from the trial), as described in the IA section (Section 3).

The design and doses tested for Part 2 will be determined according to pre-specified rules, defined in full in this SAP and Data Monitoring Committee (DMC) charter.

- a decision will be made on which dose (either 25 mg or 100 mg b.i.d.) is to be added in Part 2.

- a sample size re-estimation will be performed to determine the number of patients to be randomized in Part 2.

The sample size for Part 2 will be chosen to be in the range of 48 to 100 additional patients approximately (i.e. to aim for 40 – 85 patients completing the 90-day treatment period in Part 2 of the study). Patients who are enrolled in Part 2, either in screening or run-in phase will not receive blinded study treatment until the IA of Part 1 is completed and DMC recommends to proceed to Part 2 of the study.

- As a result of available data from interim analysis Part 1 (IA1) of the trial, Part 2 of the study will recruit approximately 50 randomized patients.

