1.4.1 Remapping rule

Subjects who received treatment as per protocol version 03 or earlier, but were assigned to an end of study day as per protocol version v04 and later (i.e., Day 270, Part 2), their end of study day will be remapped using the following rule: if the actual day of visit occurred is closer to the

planned day of end of study (i.e., Day 180, Part 1), then the planned day of end of study will be remapped to the end of study of Part 1, i.e. Day 180.

2 First interpretable results (FIR)

First interpretable results (FIR) will be provided for this trial.

Study outputs required to be created at the time of the FIR for interim and final analysis will be highlighted in Tables/Figures/Listings (TFL) shells document and marked as “Key” in the Programming Deliverables Tracker (PDT) output list.

FIR will focus on the following analyses for the final analysis:

- Subject disposition
- Demographics and baseline characteristics. Demographics and baseline characteristics include, but not limited to:
 - Age, Sex, Race, Weight, Height, BMI, Stratification factor (Asian/Non-Asian). The baseline characteristics table will include, among others, UPCR from 24hr urine collections (summary statistics as continuous variable and, by < 200 mg/mmol and \geq 200 mg/mmol group) and eGFR (summary statistics as continuous variable and, by <60 mL/min/1.73m² and \geq 60 mL/min/1.73m² group).
- Safety results
 - Number and percentage of subjects with adverse events (AEs) by body system organ class (SOC) and preferred term (PT) with a breakdown by treatment during the treatment period – Parts 1 and 2 to Day 90
 - Number and percentage of subjects with AEs by body system organ class (SOC) and preferred term (PT) with a breakdown by treatment during the treatment period – Part 2 patients on 180 days of treatment
 - Summary table of exposure adjusted treatment emergent AEs – Part 1 and Part 2
 - Number and percentage of subjects with treatment emergent serious AEs (SAEs), regardless of study drug relationship, by primary SOC and PT, with a breakdown by treatment – Parts 1 and 2 to Day 90
 - Number and percentage of subjects with treatment emergent SAEs, regardless of study drug relationship, by primary SOC and PT, with a breakdown by treatment – Part 2 patients on 180 days of treatment
 - Listing of SAEs and a listing of all AEs
 - Arithmetic mean (SD) profiles of hematology parameters over time by treatment group – Parts 1 and 2 to Day 90

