The full analysis set 1 (FAS1) will include all randomized patients in Part 1 and all randomized patients in Part 2 that consented to receive treatment as per protocol version 03 (i.e. allowing for 90 days of treatment) or earlier.

The full analysis set 2 (FAS2) will include all randomized patients in Part 2 that consented to receive treatment as per protocol version 04 or higher (i.e. allowing for 180 days of treatment). Mis-randomized patients, that is, patients who were incorrectly randomized and did not receive the study drug will be excluded from all FAS sets. For the full analysis sets, patients will be analyzed according to the treatment they have been assigned to at randomization. The full analysis sets will be used for the assessment of efficacy.

The safety analysis set (SAF) will include all randomized patients that received any study drug. The safety analysis set 1 (SAF1) will be likewise derived for patients in Part 1 and patients in Part 2 that consented to receive treatment as per protocol version 03 (i.e. allowing for 90 days of treatment) or earlier.

The safety analysis set 2 (SAF2) will be likewise derived for Part 2 that consented to receive randomized treatment as per protocol version 04 or higher (i.e. allowing for 180 days of treatment). For the safety analysis sets, patients will be analyzed according to the treatment they received.

The PK analysis set will include all subjects with at least one available valid (i.e. not flagged for exclusion) PK concentration measurement, who received any study drug and with no protocol deviations with relevant impact on PK data. For the PK analysis set, patients will be analyzed according to the treatment they received.

The PK1 analysis set will be likewise derived for patients in Part 1 and patients in Part 2 that consented to receive treatment as per protocol version 03 (i.e. allowing for 90 days of treatment) or earlier.

The PK2 analysis set will be likewise derived for Part 2 that consented to receive randomized treatment as per protocol version 04 or higher (i.e. allowing for 180 days of treatment).

The analysis sets and protocol deviation codes are related as follows:

Table 5-1: Protocol deviation codes and analysis sets

Category Deviation code	Text description of deviation	Data exclusion
Subjects are excluded from PK analysis in case of these PDs:		Exclude subject from PK, PK1 and PK2 analysis set
OTH20	Site has been closed down for GCP reasons	Yes

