Clinical laboratory evaluations

All laboratory data will be listed by treatment, subject, and visit/time and if normal ranges are available abnormalities will be flagged. A separate listing will be provided presenting all parameters in a subject with any abnormal values. Summary statistics will be provided by treatment and visit/time, for the SAF (up to Day 90) and for SAF1 and SAF2 separately. Summary statistics will include mean, SD, CV, Q1, median, Q3, minimum and maximum as appropriate. Values less than the Lower Limit (LL) will be imputed as $0.5 \times LL$ and values greater than the Upper Limit (UL) will be imputed as $1.5 \times UL$. The number and percentage of values below the LL and above the UL will be presented. For the figures, imputed values will be displayed.

Adverse events

All information obtained on adverse events will be displayed by treatment and subject. All information obtained on deaths will be likewise provided.

The overall incidence of treatment emergent AEs will be summarized by treatment group for the SAF (up to Day 90), SAF, SAF1 and SAF2 populations separately.

The number and percentage of subjects with adverse events will be tabulated by body system organ class (SOC) and preferred term (PT) with a breakdown by treatment, for the SAF (up to Day 90) and for SAF1 and SAF2 separately. A subject with multiple adverse events within a

body system is only counted once towards the total of this body system and treatment, for the event with highest severity. Summaries of SAEs will be provided in a similar manner.

A summary table of AEs leading to discontinuation of study treatment by preferred term will be produced for the SAF (up to Day 90), SAF1 and SAF2 separately.

Exposure-adjusted AE summaries will also be likewise considered for SAF.

For summary tables on exposure-adjusted AEs, the number of episodes per 100 patient months will be presented. The occurrence rate (number of episodes per 100 patient month) will be calculated as $100 \times (\text{the total number of AE episodes from all patients in the population divided by the total number of patient-months})$. A patient may have multiple occurrences of the same event. All occurrences are counted. Total patient months will be computed as $(\text{sum of the duration of exposure over patients, in days})/30.4375$. This method will account for the length of follow-up time under the assumption that events would occur with the same frequency at any point in time.

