In addition, 95% confidence intervals will be presented for the occurrence rate. It will be assumed that for each of n subjects the time t_j ($j=1, \dots, n$) represents the duration of exposure to study treatment. The sequence of occurrences of an event will be modeled to follow approximately a Poisson process with constant intensity θ . The rate parameter θ will be estimated as $\lambda = D/T$, where $T = \sum_{j=1}^n t_j$ and D is the total number of events. Conditionally on T , an exact $100 \times (1-\alpha)\%$ confidence interval for a Poisson variable with parameter θT and observed value D can be obtained based on (Garwood, 1936), from which an exact $100 \times (1-\alpha)\%$ confidence interval for $100 \times D/T$ will be derived as follows (Sahai, 1993):

Lower confidence limit $L = \frac{0.5c_{\alpha/2, 2D}}{T} * 100$ for $D > 0$, 0 otherwise,

Upper confidence limit $U = \frac{0.5c_{1-\alpha/2, 2D+2}}{T} * 100$ for $D > 0$, 0 otherwise,

where $c_{\alpha, k}$ is the α th quantile of the Chi-square distribution with k degrees of freedom.

Adverse events of special interest definitions are found in the compound electronic Case Retrieval Strategy (eCRS). The classification reflects the current version of the Development Safety Profiling Plan (DSPP) and might be updated based on review of accumulating data. A listing of the case retrieval strategy will be presented.

The frequency and percentage of patients with adverse events of special interest will be presented by MedDRA preferred term and treatment arm. These outputs will also be produced for the SAF (up to Day 90) and for SAF1 and SAF2 separately.

Further displays of AEs may be produced in order to appropriately describe the outcomes seen in this trial. For displays of Treatment Emergent events only, events will be considered as Treatment emergent if they started after the date of first administration of study treatment (or were present prior to start of study treatment but increased in severity based on preferred term) and up to 7 days after study treatment discontinuation. For post-treatment period, AEs and SAEs will be summarized separately for both SAF1 and SAF2 analysis sets.

For TEAE tables on SAF (Part 1 and Part 2 to Day 90) a cut-off of 90 + 7 days (post end of treatment) for Part 1 patients and Part 2 patients on 90 days of treatment will be used, whereas a cut-off of 90 days for Part 2 patients on 180 days of treatment will be used.

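### The exposure-adjusted AE rate is planned only on the pooled SAF, where arms differ by design in how much exposure falls after Day 90, so arms are comparable only if the AE rate is constant over time

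*SAP*

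**What the plan says.** SAP 8.2, under adverse events, sets the population: "Exposure-adjusted AE summaries will also be likewise considered for SAF". SAP section 5 defines that set: "The safety analysis set (SAF) will include all randomized patients that received any study drug". Plain SAF is not shorthand for a Day-90 set, because the same part of 8.2 summarises overall incidence "for the SAF (up to Day 90), SAF, SAF1 and SAF2 populations separately".

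The first-interpretable-results list in SAP section 2 has one matching output: "Summary table of exposure adjusted treatment emergent AEs – Part 1 and Part 2". The neighbouring AE and SAE incidence tables on that list each appear twice, once for both parts to Day 90 and once for Part 2 patients on 180 days.

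The rate is total episodes divided by total patient-months of exposure, times 100, with no stratification by part or period. The SAP says that this accounts for length of follow-up "under the assumption that events would occur with the same frequency at any point in time". Treatment-emergent events run "up to 7 days after study treatment discontinuation", while exposure ends at the last dose.

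Protocol 11.5.2 says: "Exposure-adjusted AE summaries will also be likewise considered". That sentence follows the AE tabulations for SAF (up to Day 90) and for SAF1 and SAF2 separately.

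The design has "a 90 days treatment phase in Part 1; a 180 days treatment phase in Part 2". The 100 mg arm was added after the first interim analysis and exists only in Part 2.

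**The concern.** Dividing by patient-months corrects for how much exposure an arm has, not for when in treatment that exposure falls. Here the timing differs by design. Placebo and 200 mg drew most of their patients in Part 1 (90 days), while every 100 mg patient is in Part 2 (planned 180 days). If AEs are reported more, or less, often early in treatment than late, the pooled rate differs between arms even when their risk is identical.

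The documents give one reason not to take constancy for granted. Protocol 9.1 has AEs sought by questioning at each visit, and protocol Table 8-2 has visits on Days 1, 8, 15, 30, 60 and 90, then only on Days 135 and 180. Patients may also volunteer events between visits, so this does not settle how the reported rate moves. It does mean that ascertainment is not uniform.

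At stake is one descriptive table. It is, however, on the key-results list of a dose-ranging study meant to support dose selection, and its purpose is to make arms with unequal exposure comparable.

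**Working it through.** The plan states no AE rate or expected exposure, so there is no figure of its own to reproduce beyond the Part 1 allocation: 14 + 10 + 10 + 14 = 48, as stated.

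**Inputs**
- Part 1 at 90 days: placebo 14, 10 mg 10, 50 mg 10, 200 mg 14, 100 mg 0 (protocol 3.1, SAP 1.4).
- Part 2: about 50 patients, allocated to make arms about equal over both parts (SAP 1.4). (48 + 50)/5 = 19.6 per arm, rounded here to 20. Part 2 then has about 6 placebo, 10, 10, 20 (100 mg) and 6 (200 mg).
- Assumptions: no dropout; all Part 2 patients on 180 days; the same true risk in every arm.
- *k* = AE rate in Days 91 to 180 divided by the rate in Days 1 to 90. The documents do not give it, so a range is shown.

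**Share of exposure after Day 90**
- Placebo and 200 mg: 6×90 / (14×90 + 6×180) = 540/2340 = 23%.
- 10 mg and 50 mg: 10×90 / (10×90 + 10×180) = 900/2700 = 33%.
- 100 mg: 20×90 / (20×180) = 1800/3600 = 50%.

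**Expected pooled rate, with the early rate set to 1**
- Placebo: (20 + 6*k*)/26.
- 100 mg: (1 + *k*)/2.

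| *k* | Placebo | 100 mg | 100 mg / placebo |
|---|---|---|---|
| 0.33 | 0.845 | 0.665 | 0.79 |
| 0.5 | 0.885 | 0.750 | 0.85 |
| 0.75 | 0.942 | 0.875 | 0.93 |
| 1 | 1.000 | 1.000 | 1.00 |
| 1.25 | 1.058 | 1.125 | 1.06 |
| 1.5 | 1.115 | 1.250 | 1.12 |

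With 19.6 per arm the ratios at *k* = 0.5, 1.25 and 1.5 are 0.84, 1.07 and 1.13. At *k* = 0.5, 5 to 10 placebo patients in Part 2 give 0.84 to 0.88. If 10%, 25% or 50% of Part 2 had 90-day treatment, the ratio is 0.85, 0.86 or 0.89. Against 10 mg or 50 mg it is 0.75/0.833 = 0.90.

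**Scale against sampling error.** Assume 30 episodes per 100 patient-months in Days 1 to 90 and *k* = 0.5. Placebo has 2340/30.4375 = 76.9 patient-months and 100 mg has 3600/30.4375 = 118.3. With event counts rounded to 20 and 27, the rates and the SAP's exact 95% intervals are 26.0 (15.9 to 40.2) and 22.8 (15.0 to 33.2).

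**The 7-day tail, with a constant rate.** Events gain 7 days per patient and exposure gains none. Placebo: 20×7/2340 = 6.0%. 100 mg: 20×7/3600 = 3.9%. Net ratio: 1.039/1.060 = 0.98.

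**Would the existing Day-90 rule cure it?** For SAF to Day 90, SAP 8.2 counts treatment-emergent events to 90 + 7 days in 90-day patients and to 90 days in 180-day patients. Over 90 treatment days each, with a constant rate, placebo gives (14×97 + 6×90)/(20×90) = 1898/1800 = 1.054 and 100 mg gives 1.00, a ratio of 0.95. With one Day-90 cut-off for both events and exposure, or in SAF2 alone with matched windows, the expected ratio is 1.00 for every *k*.

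**The case against.** The strongest reply is that the fair comparison is already planned. Incidence by system organ class and preferred term, SAEs, AEs leading to discontinuation and AEs of special interest are all produced for SAF (up to Day 90), SAF1 and SAF2 separately, and the Day-90 and 180-day AE and SAE tables are on the same key-results list. That stands, and it confines the problem to one descriptive table with no test or decision rule.

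It can also be said that the SAP discloses the constant-rate assumption. That stands too. A reader might infer that the adjustment fails to correct for unequal exposure, but under a constant rate it does correct for duration, apart from the tail effect of about 2%. What is missing is a check, or a version that does not need the assumption.

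A reader might also infer that the SAP breaks a protocol requirement. The text is softer than that. The protocol only says that such summaries will be considered, and its *likewise* reaches the three sets by inference. The SAP sentence keeps the same word, and the first-results list does not claim to be exhaustive. The SAP's explicit naming of SAF and the single listed table still point to one pooled rate, so the scope at least needs to be stated.

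**Conclusion.** The point holds as a low-severity one. As written, the only specified exposure-adjusted rate is the pooled SAF rate, and it compares arms with about 50% (100 mg) and 23% (placebo, 200 mg) of their exposure after Day 90. With equal risk, the 100 mg to placebo ratio is about 0.85 if the late rate is half the early one (0.84 to 0.89 across the allocations tried) and about 1.12 to 1.13 if it is 1.5 times the early one. The mismatch between event and exposure windows adds a net distortion of about 2%.

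A reader might infer that the table will make 100 mg look safer than placebo. The documents do not support that direction. They give no AE rates over time, and a rising rate would make 100 mg look worse. Either way the distortion is small relative to the confidence intervals at these arm sizes.

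The figures rest on about 20 patients per arm, no dropout and, except where varied, all Part 2 patients on 180 days. The SAP provides for Part 2 patients on 90 days but does not give their number; having more of them shrinks the effect.

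**What to change.** In SAP 8.2, name the sets that get exposure-adjusted rates, in line with protocol 11.5.2:

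1. SAF, Days 1 to 90, with one common cut-off for events and exposure in all patients. The existing 97-day and 90-day treatment-emergent cut-offs should not be carried into this table.
2. SAF1 and SAF2 separately, each with matched event and exposure windows: either stop counting events at the last dose, or add the 7 days to exposure.
3. The pooled SAF rate as an overall figure only, with a footnote that arms differ in exposure after Day 90.

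The Day-90 cut removes the imbalance in exposure period but not the one in study part, since 100 mg exists only in Part 2. Only SAF2 compares 100 mg with concurrent Part 2 placebo, and it has about 6 placebo patients: 6×180/30.4375 = 35.5 patient-months. At the assumed rates above that is 30/100 × 35.5 × 0.75, about 8 events, or 22.5 per 100 patient-months with an exact 95% interval of about 9.7 to 44.4.

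The cost is a few extra tables on analysis sets already defined, one cut-off rule specific to this output, and SAF2 rates that will be imprecise. No new data are needed.

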8.2 Descriptive analyses

All subjects within the SAF (up to Day 90), SAF1 and SAF2 will be included in the safety data analysis separately, except background and demographic characteristics which will be included in the FAS data analysis.

Subject demographics

All data for demographic variables will be listed by treatment group and subject. Summary statistics will be provided by treatment group overall.

Relevant medical history, current medical conditions, results of laboratory screens, drug tests and any other relevant information will be listed by treatment group and subject, overall and for each study part separately.

The FAS will be used for these analyses.

Baseline characteristics

All data for background variables will be listed by treatment group and subject. Baseline characteristics include but are not limited to UPCR, eGFR, and Renal biopsy information (Oxford Classification). Summary statistics will be provided by treatment group overall.

Renal biopsies used to assess study inclusion will be scored according to the Oxford classification and will be summarized descriptively by providing the frequency (n, %) of patients in the following categories:

- Mesangial score: ≤ 0.5 (M0) or >0.5 (M1)
- Endocapillary hypercellularity: absent (E0) or present (E1)

- Segmental glomerulosclerosis: absent (S0) or present (S1)
- Tubular atrophy/interstitial fibrosis: $\leq 25\%$ (T0), 26–50% (T1), or $> 50\%$ (T2)
- Cellular / fibrocellular crescents: none (C0), at least 1 (C1), in at least 25% of glomeruli (C2)

The total number of glomeruli will be also summarized separately.

UPCR and eGFR will be analyzed as continuous variables. In addition, the frequency (n, %) of patients with UPCR $< 200\text{mg}/\text{mmol}$ and $\geq 200\text{ mg}/\text{mmol}$, and eGFR $< 60\text{ mL}/\text{min}/1.73\text{m}^2$ and $\geq 60\text{ mL}/\text{min}/1.73\text{m}^2$ will be provided.

The FAS will be used for these analyses.

Treatment

Treatment exposure (days) will be summarized as a continuous variable by descriptive statistics. The duration of treatment exposure (in days) is defined as the last known date the patient took the study drug – the first day the patient took the study drug + 1, regardless of any temporary treatment interruption. Treatment exposure and reasons for discontinuation of study drug will be summarized by treatment group, for the SAF (up to Day 90) and for SAF1 and SAF2 separately.

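### The exposure-adjusted AE rate counts events for 7 days after the last dose but counts time at risk only up to the last dose (minor)

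*SAP*

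**What the plan says.** **Denominator.** In SAP 8.2 (Treatment), "The duration of treatment exposure (in days) is defined as the last known date the patient took the study drug", minus the first dose date, plus one day. SAP 8.2 (Adverse events) sums this over patients: "Total patient months will be computed as $(\text{sum of the duration of exposure over patients, in days})/30.4375". For the Poisson interval, each patient's time t_j again "represents the duration of exposure to study treatment", and T is the sum of the t_j.

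**Numerator.** The rate formula in SAP 8.2 uses "the total number of AE episodes from all patients in the population divided by the total number of patient-months" and names no event window. SAP Section 2 (First interpretable results) lists the planned output as "Summary table of exposure adjusted treatment emergent AEs", for Parts 1 and 2. SAP 8.2 defines an event as treatment-emergent "if they started after the date of first administration of study treatment", or if a pre-existing event worsened, "and up to 7 days after study treatment discontinuation". AEs in the post-treatment period are to be summarised separately.

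**Model.** The SAP says the method accounts for length of follow-up "under the assumption that events would occur with the same frequency at any point in time", and it treats the event count D as Poisson with parameter θT.

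**The concern.** D can be Poisson with parameter θT only if events are counted over the same time that T measures. Here the event window runs 7 days past the exposure window. Each patient has up to a week in which an onset adds to D while nothing is added to T. Under a constant event rate, D/T then overstates that rate, and the interval called exact is centred too high.

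The relative overstatement is larger when exposure is shorter. The arms differ in their mix of 90-day and 180-day patients, and 100 mg exists only in Part 2, so the overstatement is not quite the same in every arm. What is at stake is the level of the reported rates and, to a small degree, the comparison of 100 mg with the other arms.

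**Working it through.** The documents give no AE rate, event count or patient-month total, so there is no planned figure to reproduce. The constant 30.4375 is 365.25/12.

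**Inputs**
- Planned treatment is 90 days in Part 1 and 180 days in Part 2 (SAP 1.4).
- Part 1 allocation is 14 placebo, 10 on 10 mg, 10 on 50 mg and 14 on 200 mg. Part 2 has about 50 patients, with about equal allocation over both parts (Protocol 3.1).
- The event window ends 7 days after discontinuation, and exposure ends at last dose (SAP 8.2).

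**Assumptions**
- 48 + 50 = 98 patients, so 98/5 = 19.6 per arm.
- Every patient completes treatment, all Part 2 patients are on 180 days, and discontinuation is dated at last dose.
- Everyone is observed through the 7-day tail.
- The event rate θ is constant, as the SAP assumes.

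**Formula.** E[D] = θ × (exposure days + tail days), so the expected overstatement of D/T is tail days / exposure days. Per patient it is 7/90 = 7.8% or 7/180 = 3.9%. Per arm, the tail is 7 × 19.6 = 137.2 days.

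| Arm | Part 1 / Part 2 patients | Exposure days | 7-day tail |
|---|---|---|---|
| Placebo, 200 mg | 14 / 5.6 | 14×90 + 5.6×180 = 2268 | 137.2/2268 = 6.0% |
| 10 mg, 50 mg | 10 / 9.6 | 10×90 + 9.6×180 = 2628 | 137.2/2628 = 5.2% |
| 100 mg | 0 / 19.6 | 19.6×180 = 3528 | 137.2/3528 = 3.9% |

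**Between arms.** Placebo or 200 mg against 100 mg: 1.0605/1.0389 = 1.021. For 200 mg against placebo the ratio is 1, because the mix is the same.

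**Variations**
- *Day 1.* Read strictly, the treatment-emergent definition excludes onsets on the first dosing date, while exposure counts that day. The net excess is then 6 days: 117.6/3528 = 3.3% (100 mg) to 117.6/2268 = 5.2% (placebo, 200 mg).
- *Some Part 2 patients on 90 days.* Their number is not given. If they are 10% to 30% of Part 2, the overstatement ranges from 4.1% to 6.5% over the arms, and the largest ratio stays at about 1.02.
- *Early stopping.* If 20% of a placebo-type arm stops at Day 30, exposure is 0.8×2268 + 0.2×19.6×30 = 1932 days, and the overstatement is 137.2/1932 = 7.1% instead of 6.0%.
- *Day-90 cut-offs.* SAP 8.2 sets 97 days for 90-day patients and 90 days for 180-day patients in the Day-90 tables. No Day-90 version of the rate is stated. If one were made with exposure to Day 90 (90 × 19.6 = 1764 days), the overstatement would be 0% for 100 mg, 7×10/1764 = 4.0% for 10 and 50 mg, and 7×14/1764 = 5.6% for placebo and 200 mg.

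**Against sampling error.** Assume a rate of 30 per 100 patient-months in placebo. T = 2268/30.4375 = 74.5 patient-months, so about 22 events. The SAP's exact 95% interval is then about 18.5 to 44.7. The bias is 30 × 0.0605 = 1.8.

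**The case against.** The strongest reply is that this is a descriptive table with an openly labelled denominator. No test or decision rule uses it, the SAP says only that such summaries will be considered, and the incidence tables by system organ class and preferred term are untouched. Events per month of exposure can be read as labelled, and a shift of 1.8 inside an interval 26 wide will mislead nobody. That stands as a reason to rate the point minor. It does not remove the mismatch, because the SAP goes further than the label: it says the method accounts for follow-up time and calls the interval exact, which needs D and T over the same time.

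A reader might also infer more than the documents support:
- *Events counted to the end of study.* The rate formula names no window, and Protocol 9.1 collects AEs to the end-of-study visit. A 90-day tail would multiply rates by 1.50 (100 mg) to 1.78 (placebo, 200 mg) and make 100 mg look 16% safer than placebo. But SAP Section 2 titles the table as treatment-emergent, and SAP 8.2 puts post-treatment AEs in separate summaries. The sections read together point to the 7-day window.
- *Every reported rate is too high.* The bias holds in expectation. An event type with no onset in the tail is not inflated.
- *Arms are unequally affected within SAF1 or SAF2 alone.* With full treatment, every patient in SAF1 carries 7.8% and every patient in SAF2 carries 3.9%, whatever the arm. The inequality comes from combining the two durations, or from differential discontinuation, about which the documents give no figures.
- *Early stoppers dominate.* A patient stopping at Day 14 carries 7/14 = 50%, but adds little to sums over an arm, as the 6.0% to 7.1% example shows.

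**Conclusion.** The concern holds as a minor point. Followed as written, SAP 8.2 divides treatment-emergent episodes, counted to 7 days after discontinuation, by time that stops at last dose. The overstatement by arm is that shown in the 7-day column of the table, or the lower range if Day 1 onsets are left out. In the planned SAF table the comparison of 100 mg with placebo or 200 mg is off by about 2% at most, and 200 mg versus placebo is not affected unless discontinuation differs. These sizes rest on the allocation, full-duration and constant-rate assumptions listed above. The open numerator wording in the rate formula is a second, smaller gap that SAP Section 2 already answers.

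**What to change.** In SAP 8.2:
- Define D as treatment-emergent episodes only, replacing the unrestricted count of all episodes from all patients.
- Compute patient-months and T over the same window: exposure days + 7, cut at death, withdrawal or last contact. The alternative is to keep exposure as it is and cut D at last dose.
- Say whether Day 1 onsets count, so that both windows also start on the same day.
- If a Day-90 version is produced, apply the same cut-off to D and T for each patient.

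With matched windows the expected overstatement is 0% in every arm. The cost is two sentences and one derived variable, and the reported rates become slightly lower.
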